1 STUDY DETAILS

1.1 Study objectives

The study objectives will be assessed among 3 cohorts defined according to treatment status, these cohorts are described in Section 1.2.

The objectives of this study as well as corresponding endpoints are as follows:

Table 1. Study objectives and endpoints

Primary objective	Endpoints/Variables:
To monitor long term safety of durvalumab (all cohorts)	
 • All SAEs • Non-serious AEs that lead to dose modification, drug discontinuation, or withdrawal from the study • All Grade 3 and Grade 4 AEs • Grade 2 AEs that affect vital organs (eg, heart, liver) • Immune-mediated AEs • Laboratory findings qualifying as an SAE/AE (endpoints defined above) up until 90 days after the last dose of durvalumab in all patients
Secondary Objectives:	Endpoints/Variables:
To assess the efficacy of durvalumab in terms of ORR and DOR in patients who undergo retreatment with durvalumab (Cohort 2 only)	
ORR: Number (%) of patients with a confirmed response of CR or PR.
 
DOR: Time from first documented CR or PR to time of first documented disease progression or death in the absence of disease progression

To assess the OS of patients (all cohorts)	
OS: Time from date of randomization/date of first dose ^a in the parent clinical study until the date of death by any cause

AE adverse event; CR complete response; DOR duration of response; ORR Objective response rate; OS overall survival; PR partial response; SAE serious adverse event.

^a For randomized parent studies, the randomization date will be used in the calculation of OS. For single-arm parent studies, the date of first dose will be used in the calculation of OS.

[figure not shown]
1.2 Study design

This is a multi-center, open-label study that will enroll patients who are currently receiving durvalumab or have previously received durvalumab as monotherapy or in combination with other agents in an eligible AstraZeneca/MedImmune-sponsored clinical study (herein referred to as “a parent clinical study”).

The general study design for this study is summarized in [Figure 1](#). Patients may enroll under one of three cohorts described as follows:

- Cohort 1: includes patients who received durvalumab monotherapy or durvalumab combination therapy under the parent clinical study (including those undergoing retreatment per the parent study) who have not clinically progressed and who are eligible to continue durvalumab treatment after completing dosing of all other anticancer agents, including other investigational agents, which are a formal component of the parent study. If a patient was already retreated with durvalumab in the parent clinical study and has not progressed while on treatment, then they would be potentially eligible to enter Cohort 1; a combination treatment course initiated in the parent clinical study must be completed prior to study entry.
- Cohort 2: includes patients who completed durvalumab monotherapy or in combination with any other approved or investigational anticancer agents in a parent study, without confirmed progressive disease (PD) during the period of treatment, and who are potentially eligible for retreatment with durvalumab. The patient should not have received any other approved or investigational anticancer agents since completion of durvalumab treatment. Patients who completed the prespecified duration of treatment with durvalumab in a parent clinical study, who received clinical benefit and then subsequently experienced confirmed PD after completion of planned treatment, will be permitted to restart durvalumab treatment provided they meet the eligibility criteria. If a patient was already retreated with durvalumab in the parent clinical study and retreatment has ended, they are no longer eligible for retreatment in this study.
- Cohort 3: includes patients previously treated with durvalumab monotherapy or in combination with any other approved or investigational anticancer agents who are no longer receiving durvalumab and are not eligible to receive retreatment.

Figure 1: Study design

1.3 Number of subjects

This study will enroll patients who have been previously treated with durvalumab and/or durvalumab in combination with any other approved or investigational anticancer agents in any parent clinical study at any global site. The study will initially enroll approximately 600 patients.

2 ANALYSIS SETS

2.1 Definition of analysis sets

2.1.1 Full Analysis Set (FAS)

The FAS will include all patients enrolled in the study, regardless of the treatment received. OS analysis will be performed on the FAS. In addition, demographic and patient characteristics will be summarized amongst the FAS population.

2.1.2 Response evaluable analysis set

The response evaluable analysis set will consist of patients who are retreated with durvalumab in Cohort 2. This will be the analysis set for ORR and DOR.

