Clinical chemistry ^h		X	X	X		X	X	X	X	X
Hematology ^h		X	X	X		X	X	X	X	X
TSH (reflex free T3 or free T4) ⁱ		X	X	X		X	X	X	X	X
Pregnancy test ^j		X				X	X	X	X	X

	Follow-up before retreatment				Retreatment					
	Time since the last dose of study drug ^a			Long-term follow-up	Baseline ^b / C1	C2	C3	C4	C5 onwards ^c	
Week	Baseline/ Enrollment ^a	Day (±3 days)	Day (±7 days)		Every 3 months (±2 weeks)	0	Q4W ±3 days unless dosing needs to be held for toxicity reasons			
Day		30	60	90		1	Q28days ±3 days unless dosing needs to be held for toxicity reasons			
Monitoring										
AE/SAE assessment ^k		X	X	X		Throughout				
Survival status ^l					X					
Study drug administration										
Durvalumab (monotherapy) ^m						X	X	X	X	
Tumor assessment										
Tumor assessment ⁿ	Assessment performed according to the Investigator’s standard practice until withdrawal of consent, progression or death.					X ^o	Assessment performed according to RECIST v1.1 as determined by the Investigator (at least every 12 weeks) until withdrawal of consent, progression or death.			

- a. Follow-up visits are performed based on the duration since the last dose of study drug in either the parent clinical study or current study (whichever most recently administered the study drug). Patients who are more than 90 days beyond the last dose of study drug, will not undergo follow-up for AEs/SAEs, vital signs, concomitant medications, or laboratory safety assessments; these patients will be followed for survival and undergo tumor assessment per Investigator’s standard practice.
- b. Baseline assessments may be performed over more than 1 visit if necessary. If laboratory or imaging procedures were performed for alternate reasons prior to signing the consent, these can be used for baseline assessment purposes with consent of the patient. However, all baseline laboratory assessments must be obtained within 3 days prior to Day 1 (first retreatment visit), and baseline imaging results must be obtained within 28 days prior to Day 1 of retreatment. Baseline laboratory assessments performed within 3 days prior to Day 1 do not need to be repeated at Day 1. Patients with documented HIV test results from the parent clinical study do not need to undergo a repeat test, but HBV and HCV must be retested within the 28-day period.

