6.6 Treatment after the end of the study

AstraZeneca will continue to supply durvalumab after completion of this study, for as long as the patient is receiving clinical benefit in the opinion of the Investigator, or until the participant meets a discontinuation criteria as defined in Section 7.1.

For patients continuing to receive durvalumab treatment following the final DCO and database closure, the procedures defined in the SoA will be limited. It is recommended that the participants continue the scheduled site visits and Investigators monitor the patient's safety laboratory results periodically during treatment with durvalumab in order to manage AEs in accordance with the durvalumab Dosing Modification and Toxicity Management Guidelines (see Annex 1), and as described in Section 8.3.14.

In the event that product development reaches a point where alternative product supply options become available, then these alternative product supply options will be discussed by AstraZeneca with the Investigator. AstraZeneca will work with the Investigator to transition the patient(s) to alternative supply, where possible.

In the event that a roll-over or safety extension study is available at the time of the final DCO and database closure, patient(s) currently receiving treatment with durvalumab may then be transitioned to such a study, and the current study would reach its end. The roll-over or extension study would ensure treatment continuation with visit assessments per its protocol, as applicable. Any patient who would be eligible to move to such a study would be given a new informed consent, as applicable.

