8.2.3 Clinical endpoint assessments

Data for the following endpoints will be collected and may be evaluated as part of the analysis in the parent clinical studies from which the patients originated. Survival data will be collected in terms of OS in all patients. Efficacy variables will be collected in terms of ORR and DOR for patients in Cohort 2 who start retreatment according to clinical practice (so long as they satisfy eligibility criteria in Section 5.1). These endpoints are defined below:

- OS is defined as the time from date of randomization/enrollment in the parent clinical study until the date of death by any cause (all cohorts).
- ORR is defined as the number (%) of patients with a confirmed response of complete response (CR) or partial response (PR) from the re-initiation of treatment with durvalumab monotherapy (Cohort 2).
- DOR is defined as the time from first documented CR or PR until the time of first documented disease progression or death in the absence of disease progression (Cohort 2).

Tumor assessments, performed by the Investigator according to standard practice, to determine ORR and DOR will be collected for patients in Cohorts 1 and 2 at least every 12 weeks while the patient is receiving treatment. Assessments should be performed as deemed medically appropriate by the Investigator, for the purpose of maintaining the safety and wellbeing of the patient. Investigator reported response will be collected and summarized.

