9.2 Populations for analyses

The study population used for statistical analyses in this study is described in Table 11. Full details will be provided in the SAP.

Table 11 Population for statistical analyses

Analysis sets	Description
Full analysis set	Patients enrolled in the study.
Safety analysis set	Patients who received at least 1 dose of durvalumab on this study or enrolled on this study within 90 days of the last dose of durvalumab or durvalumab combination on the respective parent clinical study.
Response evaluable analysis set ^a	Patients who are retreated with durvalumab in Cohort 2.

^a To be performed if there is a sufficient sample size of retreated patients; otherwise, only listings will be provided.

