3 PRIMARY AND SECONDARY VARIABLES

3.1 Efficacy variables

3.1.1 Objective response rate (ORR)

ORR is defined as the percentage of patients with a confirmed investigator-assessed response of complete response (CR) or partial response (PR) from the date of re-initiation of treatment with durvalumab monotherapy. ORR will be assessed in the response evaluable analysis set (patients who are retreated with durvalumab in Cohort 2).

A confirmed response of CR/PR means that a response of CR/PR is recorded at one visit and confirmed by repeat imaging not less than 4 weeks after the visit when the response was first observed with no evidence of progression between the initial and CR/PR confirmation visit. Data obtained up until progression, or last evaluable assessment in the absence of progression, will be included in the assessment of ORR. Patients who discontinue treatment without progression, receive a subsequent anticancer therapy (note that for this analysis radiotherapy is not considered a subsequent anticancer therapy) and then respond will not be included as responders in the ORR (i.e., both visits contributing to a response must be prior to subsequent therapy for the patient to be considered as a responder).

In the case where a patient has two non-consecutive visit responses of PR, then, as long as the time between the 2 visits of PR is greater than 4 weeks and there is no PD between the PR visits, the patient will be defined as a responder. Similarly, if a patient has visit responses of CR- Not evaluable (NE), CR, then, as long as the time between the 2 visits of CR is greater than 4 weeks, then a best response of CR will be assigned.

CR and PR can be assessed using the following Electronic Case Report Form (eCRF) modules:

- **Overall Exam Assessment (OVERALL):**
 - Overall Assessment of Target and Non-Target Lesions**
 - Assess Target Lesions as a Whole (CR; PR; PD; Stable Disease [SD]/ Not Evaluable)
 - Assess Non-Target Lesions as a Whole (CR/PD/ Non-CR/Non-PD; Not Evaluable)
 - Overall Tumor Response Assessment (CR; PR; PD; SD; NED); Not Evaluable
 - Latest Scan Date for the Timepoint
 - Progression Scan Date

- **Tumor Evaluation: New Lesions and Investigator Assessment of Response (RECIST2)**

Overall visit response

- RECIST response (CR; PR; PD; SD(Non-CR/Non-PD); Not evaluable)
- Investigator's opinion agrees with RECIST response (yes/no)
- Investigator's opinion of patient status (Responding; Stable; Progressing)

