5 ANALYSIS METHODS

5.1 General principles

The below mentioned general principles will be followed throughout the study:

- Descriptive statistics will be used for all variables, as appropriate. Continuous variables will be summarized by the number of observations, mean, standard deviation(Sd), median, upper and lower quartiles minimum, and maximum. Categorical variables will be summarized by frequency counts and percentages for each category.
- Unless otherwise stated, percentages will be calculated out of the population total for the corresponding analysis set.
- For continuous data, the mean and median will be rounded to 1 additional decimal place compared to the original data. The Sd will be rounded to 2 additional decimal places compared to the original data. Minimum and maximum will be displayed with the same accuracy as the original data.
- For categorical data, percentages will be rounded to 1 decimal place.
- There are no statistical methods that will be employed to test a specific hypothesis.
- SAS® version 9.4 or later will be used for all analyses.

For efficacy endpoints (only considered for Cohort 2), the last observed measurement prior to retreatment will be considered the baseline measurement.

For safety endpoints (where all cohorts are considered) the last observation before the first dose of study treatment will be considered the baseline measurement. For assessments on the day of first dose/randomization date where time is not captured, a nominal pre-dose indicator will serve as sufficient evidence that the assessment occurred prior to first dose. Assessments

on the day of the first dose where neither time nor a nominal pre-dose indicator are captured will be considered prior to the first dose if such procedures are required by the protocol to be conducted before the first dose.

In all summaries change from baseline variables will be calculated as the post-treatment value minus the value at baseline. The percentage change from baseline will be calculated as $(\text{post-baseline value} - \text{baseline value}) / \text{baseline value} \times 100$.

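### The retreatment ORR sets no minimum potential follow-up, so Cohort 2 patients restarted shortly before the data cut-off count as non-responders and lower the ORR to the extent that such restarts occur

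*SAP*

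**What the plan says.** The denominator is every retreated Cohort 2 patient. SAP 2.1.2 reads "The response evaluable analysis set will consist of patients who are retreated with durvalumab in Cohort 2", and Protocol Table 11 has the same definition: "Patients who are retreated with durvalumab in Cohort 2". SAP 5.1 fixes the arithmetic: "Unless otherwise stated, percentages will be calculated out of the population total for the corresponding analysis set".

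The numerator is narrower. Under SAP 3.1.1 a CR or PR counts only if it is "confirmed by repeat imaging not less than 4 weeks after the visit when the response was first observed". Protocol 8.2.3 collects tumor assessments for "Cohorts 1 and 2 at least every 12 weeks while the patient is receiving treatment". That is a longest permitted interval, and SAP 5.2.2 uses unscheduled scans as well as scheduled ones.

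The time axis ends on a calendar date. Protocol 4.4 expects the study to end in Q4 2022, tied to the final DCO. A Cohort 2 patient restarts after progressing off treatment, and no last restart date is given. Under Protocol 8.3.14, SAEs are the only data reported for the study after the final DCO and database closure.

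**The concern.** The set is called response evaluable but has no condition on evaluability or follow-up. A patient who restarts a few weeks before the DCO adds one to the denominator and has little chance of adding one to the numerator. A later response in that patient is not reported, so the non-response is permanent in the study's data.

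The retreatment ORR belongs to the first-listed secondary objective. If late restarts are more than a handful, a reader cannot separate patients who did not respond from patients who did not have time to. The exact CI does not reveal this, because the recent restarts count as full observations.

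The plan's other provisions do not correct it. The sufficient-sample-size condition in SAP 5.2.2 concerns numbers, gives no threshold and ignores follow-up. SAP 5.2.4 plans a Kaplan-Meier analysis of time to response in which non-responders are censored at their last RECIST assessment. That allows for short follow-up, but it also censors patients who have progressed, so it does not yield a corrected ORR.

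**Working it through.** The documents give no expected ORR, no number retreated and no restart dates, so there is no planned figure to reproduce. What follows is an illustration under stated assumptions.

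**Inputs from the documents.** First enrolment Q3 2019 (Protocol 1.2); end Q4 2022 (Protocol 4.4); scans at most 12 weeks apart (Protocol 8.2.3); confirmation at least 4 weeks after first response (SAP 3.1.1).

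**Study span W.** Shortest, 30 Sep 2019 to 1 Oct 2022: 156.7 weeks. Middle, 15 Aug 2019 to 15 Nov 2022: 169.7 weeks. Longest, 1 Jul 2019 to 31 Dec 2022: 182.7 weeks. This is about 36 to 42 months.

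**Time needed for a confirmed response, L.**
- First scan at the 12-week limit, prompt confirmation: 12 + 4 = 16 weeks.
- Both scans at the 12-week limit: 12 + 12 = 24 weeks.
- Earlier scanning (assumed first scan at week 6): 6 + 4 = 10 weeks.

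**Assumptions.** Restarts are spread evenly over W. A patient with less than L weeks before the DCO has no confirmed response, and a patient with more has the full chance of one. The true confirmed ORR is 20%.

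**Formulas.** Share with too little time: f = L / W. Reported ORR = 20% × (1 − f).

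| W (weeks) | f, L = 10 | f, L = 16 | f, L = 24 | ORR, L = 10 | ORR, L = 16 | ORR, L = 24 |
|---|---|---|---|---|---|---|
| 156.7 | 6.4% | 10.2% | 15.3% | 18.7% | 18.0% | 16.9% |
| 169.7 | 5.9% | 9.4% | 14.1% | 18.8% | 18.1% | 17.2% |
| 182.7 | 5.5% | 8.8% | 13.1% | 18.9% | 18.2% | 17.4% |

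For L of 16 to 24 weeks, about 9-15% of the set is affected and 20% reads as about 17-18%. With f between 9% and 15%, a true 10% reads as 9.1% to 8.5%, and a true 30% as 27.3% to 25.5%.

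**Against sampling error (invented counts, exact 95% CI).**
- 6 of 30: 20.0% (7.7-38.6).
- Three late restarts without response set aside, 6 of 27: 22.2% (8.6-42.3).
- Four set aside, 6 of 26: 23.1% (9.0-43.6).

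The shift of 2 to 3 points is small beside intervals more than 30 points wide.

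**The case against.** The strongest reply is that counting everyone retreated is a recognised, conservative choice. It keeps early progressors, early deaths and dropouts as non-responders, and there is no hypothesis test for the ORR to mislead. That stands, and it is a good reason not to replace the main denominator. SAP 2.1.2 also defines the set for DOR and TTR, so editing it would change those analyses too.

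Four stronger readings are tempting, and the documents do not support them.

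- A reader might infer that the ORR is biased low as a matter of fact. That depends on how many patients restart near the DCO, which is not stated. Protocol 6.1.1 says some Cohort 2 patients may never be retreated.
- A reader might take Protocol 6.6, "For patients continuing to receive durvalumab treatment following the final DCO and database closure", as evidence of late restarts. It covers anyone still on drug, including Cohort 1 and Cohort 2 patients who restarted long before.
- A reader might treat 16 or 24 weeks as a floor. Scans may be done sooner and unscheduled scans count, so a response seen at week 6 and confirmed at week 10 is valid. Protocol Appendix C, which holds the protocol-specific RECIST requirements, is not in the text available, so scan timing could not be checked further.
- A reader might apply the arithmetic to a one-year look: 16/52 = 31% and 24/52 = 46%, so 20% would read as about 14% or 11%. Protocol 9.4 plans five annual interim analyses, but SAP 6 says none is planned. Those sections need reconciling. Until they are, the larger figures do not describe a planned analysis.

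**Conclusion.** The gap is real and its direction is certain: without a follow-up condition, recent restarts can only lower the reported ORR. Its size is not established. Under even restarts and scans at the 12-week limit, the shortfall at the final DCO is about 2 to 3 points on a true ORR of 20%. It is nearer 1 point if scanning starts at about week 6, and nil if nobody restarts in the closing weeks. It would be larger if restarts cluster late and smaller if they tail off. The even-restart assumption has no support in the documents beyond the study dates. This merits a low-cost supplementary analysis and does not invalidate the endpoint.

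**What to change.** Leave SAP 2.1.2, Protocol Table 11 and the DOR and TTR set unchanged. In SAP 5.2.2, add a prespecified ORR with exact 95% CI restricted to Cohort 2 patients whose first retreatment dose was at least 24 weeks before the DCO, with 16 weeks as an alternative cut, and show it beside the all-retreated ORR. Define the restriction by restart date alone. It must never require a post-baseline scan, because that would remove early deaths and dropouts and bias the ORR upward. Also list patients with an unconfirmed response who are still on treatment at the DCO.

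The cost is a sentence in the SAP, one table row with a smaller n and wider CI, and a short listing. The row omits outcomes already observed in recent restarts, such as early progressions, but the all-retreated row keeps them. The SAP was approved in December 2022, close to the planned end of study. The rule should therefore be recorded before retreatment responses are tabulated; otherwise the row should be labelled post hoc.

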2.1.3 Safety Analysis Set (SAS)

The SAS will consist of patients who received at least 1 dose of durvalumab on this study or enrolled on this study within 90 days of the last dose of durvalumab or durvalumab combination on the respective parent clinical study. The primary objective analysis will be assessed in the SAS.

